3.6 Rationale for Trial

Current therapies for IPF have limited efficacy (see Section 3.2), with severe side effects leading to discontinuation of treatment in 29-51% of patients demonstrated as in a real-life cohort on anti-fibrotics in North East England (Murphy et al., 2019). Hence there is a substantial medical need for new therapeutic alternatives. The current clinical trial is the first investigation of the efficacy of C21 in IPF patients. Data from the trial will guide and support the design of further clinical investigations of C21 in this indication.

3.7 Rationale for Trial Design

Given the urgent need for effective medicines in IPF, proof of concept for C21 is sought within this open-label, single-arm, multi-centre trial evaluating the safety, efficacy, and pharmacokinetics of subjects with IPF.

Since this is the first trial where patients are administered repeated doses of C21, the primary objective of the trial will be to evaluate the safety (including tolerability) of C21 in an IPF population.

Clinical Trial Protocol

Vicore Pharma AB
Trial ID: VP-C21-005

Version: 7.0
Date: 15-Sep-2021

The expected average FVC reduction in untreated IPF patients is 120 mL/24 weeks (Richeldi et al., 2014), with the same rate of decline independent of disease severity (Kolb et al., 2017) (see also Section 13.3). The consistent information on the natural course of the disease supports an open-label single-arm design. Since the individual rate of decline in lung function (FVC) is not constant, a minimum duration of IMP exposure of 24 weeks is considered necessary to investigate the efficacy of C21, with respect to demonstrating a significantly lower rate of decline in FVC than expected for this population, and durability of this response. Thus, extended treatment up to a maximum of 36 weeks may be offered as long as it is considered safe by the investigator to continue treatment, on an individual patient level.

A sample size of 60 subjects is considered sufficient for an initial investigation of safety and efficacy, whilst preventing unnecessary exposure of subjects to trial drug (see rationale for sample size regarding efficacy in Section 13.1).

3.8 Rationale for Dose and Dosing Regimen

C21 is being developed for oral treatment of IPF, a progressive, irreversible and life-threatening disease that presents a huge challenge to the patients, their families, and the health care system. The results of the Phase 1 healthy volunteer trials for C21 (C21-003; preliminary data) indicate an acceptable safety and tolerability profile for the 100 mg *b.i.d.* (bis in die; twice daily) dose.

Moreover, regular review by an Independent Data Monitoring Committee will be implemented to monitor safety during the conduct of the trial. This finding is therefore not considered to present any significant safety risk to subjects in the trial.

Overall, the safety profile of C21 as available from preclinical data and from the Phase 1 trials is interpreted as favourable for further study of the intended indication ‘Treatment of Idiopathic Pulmonary Fibrosis’.

Clinical Trial Protocol

Vicore Pharma AB
Trial ID: VP-C21-005

Version: 7.0
Date: 15-Sep-2021

3.9 Risk-Benefit Assessment

The risks to subjects in the present trial will be reduced by using C21 doses which have been evaluated in a recently completed Phase 1 trial (C21-003) (preliminary data) and found to have an acceptable safety profile; moreover centrally read telemetry data did not identify any clinically significant findings.

In addition, the risks will be minimised by strict compliance with the eligibility criteria and by close clinical monitoring. An independent data monitoring committee (IDMC) will also meet regularly to review the safety data and provide appropriate recommendations to the Sponsor on the overall safety of trial participants (see Section 14).

All subjects participating in the trial will be followed closely by medically qualified staff throughout the trial period (see Section 2 and Section 6.1). Adverse events will be carefully documented, and the subjects will receive relevant treatment should they occur.

IPF is a progressive, irreversible and fatal disease. Patients with IPF may receive benefit from stabilisation of their disease with C21.

Repetitive lung function measurement manoeuvres during the trial can lead to cough, shortness of breath, dizziness, or exhaustion, but since the subjects only carry out forced manoeuvres during clinic visits (not at home), these are always performed under medical supervision to ensure availability of medical aid if required. The assessments are part of the regular and well-established assessments for this patient population.

Furthermore, the protocol defines withdrawal criteria to secure the safety of subjects with severe progression of disease.

If the physician judges it necessary for the subject to receive a different treatment during the trial period, the subject will be withdrawn from the trial and receive relevant treatment.

Based on the above, it is considered ethically justifiable to include patients in the present trial, as the potential benefits of C21 are judged to balance possible disadvantages connected with participation in the trial.

Clinical Trial Protocol

Vicore Pharma AB
Trial ID: VP-C21-005

Version: 7.0
Date: 15-Sep-2021

4 OBJECTIVES AND ENDPOINTS

4.1 Primary Objective

To investigate the safety of C21 200 mg daily dose (100 mg *b.i.d.*) administered orally to subjects with IPF.

4.2 Secondary Objectives

To evaluate:

- The efficacy of C21 200 mg daily dose (100 mg *b.i.d.*) administered orally to subjects with IPF for 12 weeks
- The efficacy of C21 200 mg daily dose (100 mg *b.i.d.*) administered orally to subjects with IPF for 24 weeks
- The efficacy of C21 200 mg daily dose (100 mg *b.i.d.*) administered orally to subjects with IPF for 36 weeks
- The pharmacokinetic (PK) profile of C21 200 mg daily dose (100 mg *b.i.d.*) after multiple dosing

4.3 Exploratory Objectives

To investigate a range of laboratory parameters as potential biomarkers of inflammation, proliferation and fibrosis following oral administration of C21 200 mg daily dose (100 mg *b.i.d.*).

4.4 Primary Endpoint

Nature and frequency of adverse events occurring over the trial period.

4.5 Secondary Endpoints

- Change from baseline in forced vital capacity (FVC) value over 12, 24, and 36 weeks
- Plasma concentration of C21 and derived PK parameters evaluated in a sub-set of subjects

4.6 Exploratory Endpoints

Blood samples will be saved for potential future analyses of biomarkers reflecting fibrosis and inflammation.

Clinical Trial Protocol

Vicore Pharma AB
Trial ID: VP-C21-005

Version: 7.0
Date: 15-Sep-2021

5 TRIAL POPULATION

5.1 Inclusion Criteria

- 1) Written informed consent, consistent with ICH-GCP R2 and local laws, obtained before the initiation of any trial related procedure
- 2) A diagnosis of IPF within 5 years prior to Visit 1, as per either ATS/ERS/JRS/ATLAT/Fleischner guidelines ([Raghu et al., 2018](#); [Lynch et al., 2018](#))
- 3) Age ≥ 40 years
- 4) FVC $\geq 60\%$ predicted at Visit 1 and 2 (*Specific for UK*: FVC $\geq 80\%$ predicted at Visit 1 and 2 or FVC $> 60\%$ predicted at Visit 1 and 2 for subjects previously treated with antifibrotic treatment e.g., nintedanib and/or pirfenidone, or refused such treatments)
- 5) FEV1/FVC ratio ≥ 0.7 prebronchodilator at Visit 1 and 2
- 6) Oxygen saturation (SpO₂) $> 85\%$ by pulse oximetry while breathing ambient air at rest at Visit 1
- 7) High-resolution computed tomography (HRCT) within 36 months prior to Visit 1 with central reading demonstrating either a or b, and c:
 - a. A pattern consistent with usual interstitial pneumonitis (UIP) according to ATS/ERS/JRS/ALAT or Fleischner guidelines ([Raghu et al., 2018](#); [Lynch et al., 2018](#))
 - i. UIP
 - ii. Probable UIP or
 - b. A pattern indeterminate for UIP according to either ATS/ERS/JRS/ALAT or Fleischner guidelines ([Raghu et al., 2018](#); [Lynch et al., 2018](#)) and a historical biopsy consistent with IPF
 - c. Extent of fibrosis $>$ extent of emphysema
- 8) Fully vaccinated against COVID-19 prior to screening (Visit 1). Subjects are considered fully vaccinated for COVID-19 ≥ 14 days after they have received vaccination dose(s) according to local label

Clinical Trial Protocol

Vicore Pharma AB
Trial ID: VP-C21-005

Version: 7.0
Date: 15-Sep-2021

5.2 Exclusion Criteria

- 1) Previous use of antifibrotic treatment for an interstitial lung disease (e.g. nintedanib or pirfenidone) for >6 months
- 2) Smoking (including e-cigarettes) within 6 months prior to Visit 1
- 3) Body mass index (BMI) >35 or <18
- 4) IPF exacerbation within 3 months prior to Visit 1, as defined by [Collard et al. \(2016\)](#):
 - Acute worsening or development of dyspnoea typically <1 month duration
 - Computed tomography with new bilateral ground-glass opacity and/or consolidation superimposed on a background pattern consistent with usual interstitial pneumonia pattern (if no previous computed tomography is available, the qualifier “new” can be dropped)
 - Deterioration not fully explained by cardiac failure or fluid overload
- 5) Concurrent serious medical condition with special attention to cardiac or ophthalmic conditions (e.g. contraindications to cataract surgery), or moderate to severe hepatic impairment, which in the opinion of the investigator makes the subject inappropriate for this trial
- 6) Malignancy within the past 5 years with the exception of *in situ* removal of basal cell carcinoma and cervical intraepithelial neoplasia grade I
- 7) Treatment with any of the medications listed below within 4 weeks prior to Visit 1:
 - Strong CYP3A4 inducers (e.g. rifampicin, phenytoin, St. John’s Wort)
 - Strong CYP3A4 inhibitors (e.g. clarithromycin, ketoconazole, nefazodone, itraconazole, ritonavir)
 - Medicines that are substrates of CYP1A2, CYP3A4 or CYP2C9 with a narrow therapeutic range
 - Experimental drugs
 - Antifibrotic treatment
 - Any systemic immunosuppressive therapies other than:
 - Inhaled corticosteroids which can be used throughout the trial period provided the dose is kept stable
 - Corticosteroids for the treatment of acute exacerbations
 - The continuation of a stable daily dose of ≤ 15 mg prednisolone, or equivalent
- 8) Treatment with any of the medications listed below within 2 weeks prior to Visit 1:
 - Proton pump inhibitors (PPIs) more than once daily
 - Histamine H2 receptor antagonists (H2RAs)
 - Sulphasalazine and rosuvastatin

Clinical Trial Protocol

Vicore Pharma AB
Trial ID: VP-C21-005

Version: 7.0
Date: 15-Sep-2021

- High dose breast cancer resistance protein sensitive substrates (other than sulphasalazine or rosuvastatin)

9) Any of the following findings at Visit 1:

- Prolonged QTcF (QT interval with Fridericia's correction) (>450 ms), clinically significant cardiac arrhythmias or any other clinically significant abnormalities in the resting ECG, as judged by the investigator
- Increased AST or ALT >3 times Upper Limit of Normal (ULN), or bilirubin >1.5 times ULN
- Positive results for hepatitis B surface antigen (HBsAg), hepatitis C virus antibody (HCVAb) or human immunodeficiency virus 1+2 antigen/antibody (HIV 1+2 Ag/Ab)
- Positive serum pregnancy test (minimum sensitivity 25 IU/L or equivalent units of human chorionic gonadotropin [HCG])

10) Inability to generate lung function data at Visit 1 meeting the minimum standards of the ATS/ERS 2005 guideline ([Miller et al. 2005](#)), as determined by central review

11) Clinically significant abnormal laboratory value at Visit 1 indicating a potential risk for the subject if enrolled in the trial as evaluated by the investigator

12) Pregnant or breast-feeding female subjects

13) Female subjects of childbearing potential not willing to use contraceptive methods as described in Section [5.3.1](#)

14) Male subjects not willing to use contraceptive methods as described in Section [5.3.1](#)

15) Subjects not willing to adhere to dietary restrictions during the trial period as described in Section [5.4](#)

16) Participation in any other interventional trial during the trial period

17) Subjects known or suspected of not being able to comply with this trial protocol (e.g. due to alcoholism, drug dependency or psychological disorder)

18) Discontinuation or change of previous antifibrotic treatment (e.g. nintedanib or pirfenidone) due to disease progression

Clinical Trial Protocol

5.3 Restrictions During the Trial

5.3.1 Contraception Requirements

Women of child bearing potential must practice abstinence (if that is their preferred lifestyle) from Visit 1 to Visit 15, or must agree to use a highly effective method of contraception with a failure rate of <1% to prevent pregnancy (combined [oestrogen and progestogen containing] hormonal contraception associated with inhibition of ovulation [oral, intravaginal, transdermal], progestogen-only hormonal contraception associated with inhibition of ovulation [oral, injectable, implantable], intrauterine device or intrauterine hormone-releasing system) from at least 4 weeks prior to first IMP administration to 4 weeks after last IMP administration. Their male partner must agree to use a condom during the same time frame, unless he has had a demonstrated successful vasectomy more than 6 months prior to first IMP administration.

Males should use condom and their female partner of child-bearing potential must use a contraceptive method with a failure rate of <1% to prevent pregnancy (see above) and drug exposure of a partner and refrain from donating sperm from the date of dosing until 3 months after the last IMP administration.

5.4 Dietary Restrictions

In relation to IMP administrations, subjects should adhere to restrictions regarding food intake:

- No food intake for 2 hours prior to taking the C21 capsules
- No food intake for 1 hour after taking the C21 capsules

Once daily PPIs must be taken 1 hour after the morning dose of C21

5.5 Screening failure

A screen failure occurs when a subject who consents to participate in the clinical trial is not subsequently assigned to IMP. A minimal set of screen failure information is required to ensure transparent reporting of screen failure subjects to meet the Consolidated Standards of Reporting Trials publishing requirements and to respond to queries from regulatory authorities. Minimal information includes demography, screen failure details, eligibility criteria, and any SAE.

Individuals who do not meet the criteria for participation in this trial (screen failure) can only be rescreened after discussion with the Medical Monitor.

5.6 Withdrawal Criteria

5.6.1 Evaluation for Withdrawal after each 12 Week Treatment Period

After completion of each 12-week treatment period, the investigator will make a medical evaluation and decide if the subject may continue into the next 12-week treatment period. The decision will be based on:

- No immediate need for other antifibrotics
- A positive risk/benefit balance

Clinical Trial Protocol

Vicore Pharma AB
Trial ID: VP-C21-005

Version: 7.0
Date: 15-Sep-2021

Failure to pass the medical evaluation will result in the subject being withdrawn from the trial (see Section 5.4.2).

5.7 Withdrawal from Trial

A subject will be withdrawn from trial if any of the following occurs:

- A decline from baseline in FVC value of > 10% predicted on 2 consecutive occasions and an FVC <60% predicted (*Specific for UK*: FVC <80 % predicted ; or FVC <60% predicted for subjects previously treated with nintedanib and/or pirfenidone, or refused such treatments)
- A decline from baseline in FVC value of 5-10% predicted on 2 consecutive occasions and worsening of respiratory symptoms and FVC <60% predicted (*Specific for UK*: FVC <80 % predicted; or FVC <60% predicted for subjects previously treated with nintedanib and/or pirfenidone, or refused such treatments)
- Consistent failure to comply with dietary requirements in Section 5.4, according to the investigators
- The investigator judges it necessary due to medical reasons
- Failure to pass the medical evaluation after each 12-week treatment period (see Section 5.6.1)
- It is the wish of the subject to withdraw for any reason
- Pregnancy

An end-of-trial visit (Visit 15) must be completed for all subjects withdrawn from the trial.

Subjects withdrawn due to pregnancy will be followed – as consented to – until termination or delivery and the infant must be followed at least until the age of one month.

Subject who withdraws prior to week 12 will be replaced until 60 subjects have completed the 12-week visit.

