6.4 Trial Duration and Participating Centers

Planned first subject screened: Q3 2020

Planned last subject enrolled: Q1 2022

Planned last subject last visit: Q1 2023

The end of trial date is defined as the date the last subject attends the last visit.

The trial will be conducted at trial sites globally.

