10 CHANGES TO TRIAL CONDUCT

10.1 Protocol Amendments

Before implementation of substantial changes (as defined in EU guidance documents [[European Commission 2006, 2010](#)]) unless considered an Urgent Safety Measure, approval/favourable opinion must be obtained from the appropriate regulatory authority(ies) and IEC(s).

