13.1 Sample Size and Power Considerations

Sample size is based on assumptions of a 40 mL decline in FVC/24 weeks and a standard deviation of 200 mL. With 55 evaluable subjects there is a 90% power that the 90% confidence interval for the decline in FVC at 24 weeks exclude the value 120 mL, a value considered to represent the natural course decline in 24 weeks for an untreated subject. The total of 60 subjects will be included to compensate non-evaluable subjects for reasons such as early drop out.

Analysis Data Sets

The full analysis set (FAS) will consist of all subjects who have received at least one dose of IMP and who has at least one post-baseline assessment of efficacy.

The per protocol analysis set (PPAS) will be a subset of FAS and consist of all subjects without any major protocol deviations that are judged to compromise the analysis of the data and with data collection up to at least week 24. All protocol deviations will be judged as major or minor prior to database lock.

The safety analysis set (SAS) will consist of all subjects who have received at least one dose of IMP.

The pharmacokinetic (PK) dataset will consist of all subjects selected for PK assessments and with at least one post-dose plasma sample analysed.

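### Protocol 5.7: the 10% upper limit in the second FVC withdrawal criterion leaves a small gap, so declines of 12 then 9 points with symptoms meet neither FVC criterion while 7 then 7 does

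*Combined protocol and SAP*

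**What the plan says.** Section 5.7 withdraws a subject when any one item on a list occurs. Two items concern FVC:

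- **First FVC criterion:** "A decline from baseline in FVC value of > 10% predicted on 2 consecutive occasions", together with FVC below the floor. Symptoms are not required.
- **Second FVC criterion:** "A decline from baseline in FVC value of 5-10% predicted on 2 consecutive occasions and worsening of respiratory symptoms", together with FVC below the same floor.

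The floor is 60% predicted. In the UK it is 80%, or 60% for subjects who had or refused antifibrotics. Nothing in the protocol says that the second band means 5% or more, or how to treat one reading above 10 followed or preceded by one between 5 and 10.

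Other routes to withdrawal also apply:

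- **Medical reasons (5.7):** "The investigator judges it necessary due to medical reasons".
- **Need for a different treatment (3.9):** "the subject will be withdrawn from the trial and receive relevant treatment".
- **12-weekly evaluation (5.6.1):** "Failure to pass the medical evaluation will result in the subject being withdrawn from the trial".

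Section 13.3.1 will summarise the number of rapid decliners, identified by reference to the withdrawal criteria.

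**The concern.** Each criterion requires both consecutive readings to lie in its own band. A pair with one reading in each band therefore satisfies neither, although every reading in it shows a decline of at least 5 points and one exceeds 10. With the same symptoms and floor, the rule withdraws at 7/7 and not at 12/9, so the milder course triggers it and the worse one does not.

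At stake is when a progressing, symptomatic subject is withdrawn under a stated criterion. In the gap, withdrawal depends on another route or on the next reading, 2 to 4 weeks later by the visit schedule. If the rapid-decliner count in 13.3.1 refers only to the two FVC bullets, it inherits the same ordering. No bias in mean FVC change under the current wording is claimed.

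**Working it through.** The plan gives no figure for this rule, so the check is of its logic, followed by a rough size.

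**Rule as written.** Let d1 and d2 be consecutive declines in percentage points of predicted FVC.

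- C1: d1 > 10 and d2 > 10, below the floor.
- C2: 5 ≤ d1 ≤ 10 and 5 ≤ d2 ≤ 10, symptoms worse, below the floor.

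With symptoms worse and the floor condition met:

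| d1, d2 | C1 | C2 | Withdrawn on FVC? |
|---|---|---|---|
| 7, 7 | no | yes | yes |
| 12, 12 | yes | no | yes |
| 12, 9 | no (9 is not > 10) | no (12 is outside 5-10) | no |
| 9, 12 | no | no | no |

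On whole-number pairs from 5 to 20 there are 6 values in 5-10 and 10 above 10, so 2 × 6 × 10 = 120 of 16 × 16 = 256 pairs meet neither. Every one straddles 10. This describes the grid, not how often patients fall there.

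**Is it attainable?** Yes. A baseline of 66% predicted meets the general entry criterion (5.1). Readings of 57% then 54% give declines of 9 and 12, both below 60%, and neither criterion is met. Readings of 59% and 59% give 7 and 7, and C2 is met. In a straddling pair the smaller decline is at most 10, so if both readings must be below 60% the baseline must be under 70%. The gap therefore covers baselines of 60 to <70%, or 80 to <90% under the UK 80% floor.

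**Does it close?** Often. The sequences 12, 9, 9 and 9, 12, 13 are captured at the third reading. The sequence 12, 9, 12, 9 never is.

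**Size.** From 13.1: "Sample size is based on assumptions of a 40 mL decline in FVC/24 weeks and a standard deviation of 200 mL". The other inputs are assumptions, because the protocol does not give them:

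- 25 to 40 mL per percentage point and a visit-to-visit SD of 1.5 to 3 points.
- Baseline uniform over 60-80% predicted, with the 60% floor required at both readings.
- 12 on-treatment readings (Visits 3-14), with true decline either constant or linear in time.

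True decline in points = Normal(40, 200) / (mL per point); reading = true decline + Normal(0, SD). The literal rule is compared with a rule that needs both declines ≥ 5, using the same floor. Expected numbers out of 60, before symptoms are required:

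- Captured late or never: about 0.8 to 3.2 (0.8/60 = 1.3% to 3.2/60 = 5.3%).
- Never captured: about 0.07 to 0.5 with constant decline and 0.26 to 0.8 with linear decline, so 0.07 to 0.8 overall.
- Median delay among those captured later: 4 to 5 weeks.

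**The case against.** The strongest reply is that the gap rarely matters in practice. A symptomatic subject below the floor with one decline above 10 points is the kind of subject the medical-reasons item exists for, and withdrawal is mandatory once the investigator so judges. The need for other treatment, the evaluations at weeks 12 and 24, and spirometry at every visit add cover. The two bullets can also be read as tiers, with a larger decline needing no symptoms and a smaller one needing them; on that reading a 12-point decline passes the lower threshold. That is probably how many sites would apply it.

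Most of this stands and is why the point is minor. The tiered reading, however, is not in the text, which states an explicit upper limit. If it is what was meant, the edit only makes it explicit.

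Three stronger readings are tempting, and the documents do not support them:

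- A reader might infer that these subjects cannot be withdrawn. They can, by any of the other routes.
- A reader might infer that the FVC criteria were meant to act without judgement. The protocol does not say so, and the second criterion itself requires someone to judge that symptoms have worsened, with no scale given.
- A reader might infer that the rapid-decliner count is wrong. Section 13.3.1 refers to the withdrawal criteria generally, so the count is affected only if it means the two FVC bullets.

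An asymptomatic 12/9 pair is not part of the point, since the lower band requires symptoms.

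**Conclusion.** The wording of 5.7 is wrong at one boundary, and the matter is minor. The logical gap follows from the text alone, with high confidence. Its size rests on assumed measurement noise, mL per point, baseline distribution and shape of decline, and on reading percent predicted as absolute points. Under those assumptions about 0.8 to 3.2 of 60 subjects would be captured late or never by the FVC criteria, and fewer than one never. Requiring symptoms lowers both figures, and the other withdrawal routes limit the consequence further. The usual result is a delayed criterion-based withdrawal, not a subject left without protection.

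**What to change.** In the second FVC bullet of 5.7, replace the 5-10% predicted band with a decline of at least 5% predicted. Keep the two consecutive occasions, the worsening symptoms and the existing floor. Outcomes for pairs such as 6/6 and 12/12 do not change; only straddling pairs with symptoms below the floor are added.

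The cost is one edited bullet and no new data. It belongs in the next amendment. Section 10.1 requires approval "Before implementation of substantial changes", so regulators and ethics committees come first if the edit is deemed substantial. Section 6.4 gives "Planned last subject enrolled: Q1 2022", so some subjects would already have been followed under the existing wording.

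The downside is slightly more mandatory withdrawals. Those before week 24 are imputed at 60 mL/12 weeks (13.3.1, 13.3.4.1), which may be slower than these subjects' own course. At 25 mL per point, a fall of 9 points over a full 24 weeks is 9 × 25 = 225 mL, or 112.5 mL/12 weeks. One such subject among 60, withdrawn 12 weeks early, would move the week-24 mean by (112.5 − 60)/60 ≈ 0.9 mL. The edit could therefore flatter that mean very slightly, which is not a reason to keep the gap.
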